5.5.1 Emergency Unblinding

If a participant experiences an AE whose management (e.g., diagnostic procedures, treatment) in the opinion of the principal investigator (PI) or designee would differ depending on the study arm, or in the case of pregnancy of a participant's partner, then the PI or designee will contact the NIH CC Pharmacy for release of the randomization code. The sponsor and data and safety monitoring board (DSMB) executive secretary will be informed within 1 business day of any request for unblinding. The participant will remain enrolled in the study and the data will be used for analysis.

5.6 Concomitant Medications and Procedures

All concomitant medications, including those received within 28 days before the administration of pembrolizumab, will be recorded in the Clinical Research Information Management System of the NIAID (CRIMSON), including all prescription, over-the-counter, herbal supplements, and IV medications and fluids. For this protocol, a prescription medication is defined as a medication that can be prescribed only by a properly authorized/licensed clinician. If changes occur during the study period, then documentation of drug dosage, frequency, route, and date may also be included in CRIMSON.

5.7 Prohibited Medications and Procedures

Treatment with systemic corticosteroids, other immunomodulatory drugs, or other drugs targeting PD-1, PD-L1, or PD-L2 will not be permitted during the first 48 weeks of the study except as summarized below, unless discussed with and approved by the PI or designee.

Participants are prohibited from receiving the following therapies during the first 48 weeks of the study:

- Immunotherapy not specified in this protocol (e.g., cyclosporine, tacrolimus, mycophenolate mofetil, azathioprine, sirolimus, therapies targeting tumor necrosis factor- α).
- Investigational agents other than pembrolizumab or expanded access ARVs.
- Any vaccine within 30 days pre-dose and through week 16, and live vaccines through week 48 in this study. Examples of live vaccines include, but are not limited to, the following: measles, mumps, rubella, varicella/zoster, yellow fever, rabies, Bacillus Calmette–Guérin, and typhoid.

Note: Seasonal influenza vaccines for injection are generally inactivated flu vaccines and are allowed after week 16; however intranasal influenza vaccines (e.g., Flu-Mist[®]) are live attenuated vaccines, and are not allowed.

- Systemic corticosteroids for any purpose other than to modulate symptoms from an event of clinical interest (ECI) of suspected immunologic etiology.

Participants who, in the assessment of the investigator, require the use of any of the aforementioned treatments for clinical management after receiving the single dose of pembrolizumab will continue to be followed in the study. Participants may receive other medications that the investigator deems to be medically necessary.

5.8 Management of Study Drug-related AEs

In the event of AEs related to the study drug, participants will receive appropriate supportive care measures as deemed necessary by the treating investigator. Given that management may depend on knowledge of the underlying treatment arm, as noted above, the PI or designee may unblind (see emergency procedure for unblinding) to ensure that the diagnostic evaluations and therapeutic interventions are directed appropriately. Suggested supportive care measures for the management of pembrolizumab-related AEs with potential immunologic etiology are outlined in Appendix A. Where appropriate, these guidelines include the use of oral or IV treatment with corticosteroids as well as additional anti-inflammatory agents if symptoms do not improve with administration of corticosteroids. Note that several courses of steroid tapering may be necessary as symptoms may worsen when the steroid dose is decreased. For each disorder, attempts should be made to rule out other causes such as bacterial or viral infection, which might require additional supportive care. The treatment guidelines are intended to be applied when the investigator determines the events to be related to pembrolizumab.

Note: if after the evaluation, the event is determined not to be related, the investigator does not need to follow the treatment guidance (as outlined in Appendix A).

It may be necessary to perform conditional procedures such as bronchoscopy, endoscopy, or skin photography as part of standard clinical evaluation of the event.

6 Study Schedule

NOTE: Five participants will be enrolled initially and followed for 90 days for safety outcomes. No additional participants will be enrolled until the DSMB has reviewed the 90-day safety data and recommended that the protocol can resume enrollment.

All study visits will be done at the NIH CC. A table of the study schedule is presented in [Appendix B](#).

6.1 Screening (week -6 to 0)

The participant will sign the informed consent form for this study before undergoing any procedure or evaluation. Screening procedures/evaluations to determine eligibility for this study are listed below. These procedures may occur over more than 1 visit.

- Physical exam with vital signs.
- Review medical and medication history, including past and current ART regimens.
- For participants of reproductive potential, counseling concerning the importance of consistently using two forms of effective birth control in light of the potential risk of pembrolizumab to a developing fetus.
- Blood draw for clinical lab evaluations: complete blood count with differential (CBC/diff), prothrombin/partial thromboplastin time, chemistry panels (acute, hepatic, and mineral), lipid panel, TSH and T4, ACTH, cortisol, hemoglobin A1c, TB QuantiFERON Gold, HIV serology (if not previously documented at NIH), plasma HIV viral load, immune profile including CD4 count, HBV testing (DNA, surface antigen, and antibody), and HCV testing (RNA and antibody).
- Urinalysis.
- Pregnancy test (serum or urine, for participants of childbearing potential only).
- Electrocardiogram.
- HLA typing (unless previously performed at NIH).
- Collection of cells/serum/plasma for research and stored samples.
- Leukapheresis to store cells for research studies, after eligibility is confirmed. If leukapheresis cannot be performed for technical or other reasons (e.g., poor venous access or other contraindication to the procedure), then an additional 80 mL of blood will be drawn.

6.2 Baseline (day 0)

- At baseline, blood for baseline safety and research labs will be drawn. For participants of childbearing potential only, pregnancy test (serum or urine) will be obtained,
- For participants of reproductive potential, counseling concerning the importance of consistently using two forms of effective birth control in light of the potential risk of pembrolizumab to a developing fetus.

Participants will be randomized and will receive either a single 200-mg dose of pembrolizumab or placebo via IV infusion. The infusion will be administered over at least 30 minutes, and the participant will be monitored throughout and for 2 hours after for any signs of infusion or allergic reactions. Infusion-related reactions will be managed

as summarized in [Appendix A](#). If the infusion is discontinued due to an infusion-related reaction, it will not be resumed.

6.3 Follow-up (weeks 1-96)

Participants will return for follow-up visits at weeks 1, 2, 3, 4, 6, 9, 12, 16, 24, 36, and 48. All visits through week 6 will have a window of ± 4 days; visits from week 9 onward will have a window of ± 7 days. At all visits, participants will have the following:

- Review of medical and medication history.
- Targeted physical exam, including weight, vital signs, and a symptom-directed evaluation.
- Assessment of AEs.
- For participants of reproductive potential, counseling concerning the importance of consistently using two forms of effective birth control in light of the potential risk of pembrolizumab to a developing fetus.
- Blood draw for clinical and research evaluations (see [Section 7](#)).
- Pregnancy test (serum or urine, for participants of childbearing potential only).
- Optional follow-up leukapheresis at weeks 3 or 4 and 12. Refusal to undergo leukapheresis will not otherwise affect participation in the study.

Follow-up telephone calls at weeks 60, 72, 84, and 96 (± 2 weeks) will be conducted to see if any AEs potentially related to pembrolizumab occurred during the prior 12 weeks. Participation in this study will end after the week 96 call.

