Accrual Period:	2 years
Study Duration:	Start Date: January 2018 End Date: January 2022 Total length of individual participation: Up to 102 weeks
Study Design:	Randomized, double-blind, placebo-controlled study. Twenty HIV-infected patients with poor immunologic response will be randomized 3:1 to receive a single dose of either pembrolizumab or placebo and be followed for safety for 96 weeks. Blood will be drawn at each visit for research evaluations. Participants will undergo leukapheresis at screening (after confirmation of eligibility), with optional leukapheresis at weeks 3-4 and 12.
Study Agent/ Intervention Description:	Pembrolizumab, 200 mg, or placebo via intravenous (IV) infusion, single dose.
Primary Objective:	To evaluate safety and tolerability of a single dose of pembrolizumab in people with HIV infection and poor immunologic response.

- Secondary Objective:** To evaluate the expression of PD-1 on CD4+ and CD8+ T cells following a single dose of pembrolizumab.
- Primary Endpoint:** Frequency of either Grade 3 or higher adverse events or Grade 2 or higher autoimmune events requiring corticosteroid therapy that are possibly, probably, or definitely related to pembrolizumab.
- Secondary Endpoint:** Magnitude and duration of decreased expression of PD-1 relative to baseline levels on lymphocytes.

Précis

A subset of HIV-infected patients, those with poor immunologic response to combined antiretroviral therapy (CD4+ T-cell count of less than 300-350 cells/mm³) despite control of viremia, are at increased risk for both HIV-related and non-HIV-related complications compared to immunologic responders. Thus, novel approaches for treating HIV infection are needed to facilitate management of this patient population.

One potential drug target for HIV treatment is the T-cell receptor PD-1. Binding of PD-1 to its ligands, PD-L1 and PD-L2, inhibits proliferation of T cells and production of cytokines. This naturally serves to dampen potentially harmful excessive immune responses. Upregulation of PD-1 and/or its ligands can be observed in tumors and people with chronic viral infection, including HIV. This upregulation can inhibit T-cell immune surveillance, which may result in tumor growth or poor control of infection.

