Pembrolizumab inhibits an immune checkpoint, and thus there is the potential for development of immune-related complications. Treatment-emergent immune-mediated diseases have been observed in cancer trials, and include pneumonitis, colitis, hepatitis, hypophysitis, thyroid disorders (hyper- and hypothyroidism, and thyroiditis), type 1 diabetes mellitus (DM), and nephritis and renal dysfunction (Table 1).²⁷ Rare potentially immune-mediated diseases include uveitis (0.5%) and other ocular disorders, myositis (0.5%), pancreatitis (0.3%), arthritis (1.5%), and Guillain-Barre syndrome (0.1%). There have been rare reports of primary adrenal insufficiency, hypoparathyroidism, myasthenia gravis, vasculitis, hemolytic anemia, autoimmune thrombocytopenia, hemophagocytic lymphohistiocytosis, systemic inflammatory response syndrome, histiocytic necrotizing lymphadenitis, sarcoidosis, gastritis, duodenitis, polymyalgia rheumatica, meningitis, myelitis, encephalitis and other neurologic disorders, pericarditis, myocarditis, some of which have been fatal, as well as severe skin reactions including Stevens-Johnson syndrome, toxic epidermal necrolysis (some cases with fatal outcome), exfoliative dermatitis, and bullous pemphigoid. Onset of immune-mediated complications typically occurred between 1 and 5 months, though onset has been reported as early as 1 day and as late as 21 months after initiation of pembrolizumab, and can occur after discontinuation of the drug.²⁷ Management (Appendix A) includes treating with corticosteroids (e.g., prednisone, 1-2 mg/kg/day followed by a taper); hypothyroidism may be treated with levothyroxine. Very rarely, immune-mediated pneumonitis has been fatal.

Of the 2799 patients treated with pembrolizumab in the Merck Reference Safety Dataset, there were 10 deaths attributed to the drug: respiratory failure (n = 1), cardio-respiratory arrest (n = 1), interstitial lung disease (n = 1), general physical health deterioration (n = 1), myocardial infarction (n = 1), pneumonia (n = 2), and pneumonitis (n = 3).²⁷

Table 1. Immune-mediated Adverse Reactions

Adverse Reaction	All Grades (%)	Grade 2 (%)	Grade 3 (%)	Grade 4 (%)	Grade 5 (%)
Hypothyroidism	8.5	6.2	0.1	0	0
Hyperthyroidism	3.4	0.8	0.1	0	0
Pneumonitis	3.4	1.3	0.9	0.3	0.1
Colitis	1.7	0.4	1.1	< 0.1	0
Hepatitis	0.7	0.1	0.4	< 0.1	0
Hypophysitis	0.6	0.2	0.3	< 0.1	0
Nephritis	0.3	0.1	0.1	< 0.1	0
Type 1 diabetes mellitus	0.2	< 0.1	0.1	0.1	0

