12.1 Documenting, Recording, and Reporting Adverse Events

All AEs occurring from the time of the initial leukapheresis through week 48 will be documented, recorded, and reported. If no leukapheresis is performed, then all AEs occurring from the time of pembrolizumab administration through week 48 will be documented, recorded, and reported. Between weeks 48 and 96, reporting will be limited to only those SAEs and autoimmune events that are possibly, probably, or definitely related to pembrolizumab.

At each contact with the participant, information regarding AEs will be elicited by appropriate questioning and examinations and will be:

- documented in the participant's medical record/source document,
- recorded in CRIMSON, and
- reported as outlined below (e.g., IND sponsor and FDA).

If a diagnosis is clinically evident (or subsequently determined), then the diagnosis rather than the individual signs and symptoms or lab abnormalities will be recorded as the AE.

All abnormal laboratory findings will be reviewed on a routine basis by the PI to identify potential safety signals. An abnormal lab not included on the toxicity table should be assessed in a similar fashion to the criteria above.

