Appendix B: Schedule of Procedures and Evaluations

Evaluation	Study week (day window)														Early termination visit
	Screening ^a Week -6 to 0	Baseline Day 0	1 (± 4)	2 (± 4)	3 (± 4)	4 (± 4)	6 (± 4)	9 (± 7)	12 (± 7)	16 (± 7)	24 (± 7)	36 (± 7)	48 (± 7)	60, 72, 84, 96 (all ± 14)	
Informed consent	X														
Physical exam with vital signs	X		X	X	X	X	X	X	X	X	X	X	X		X ^b
Medical history/medication review	X		X	X	X	X	X	X	X	X	X	X	X	X ^c	X ^d
Counseling on use of birth control	X	X	X	X	X	X	X	X	X	X	X	X	X	X	X ^c
Blood draw for screening labs	X														
Urinalysis	X														
Urine Pregnancy t(for participants of childbearing potential only)	X	X	X	X	X	X	X	X	X	X	X	X	X		
ECG	X														
HLA typing	X														
Blood draw for storage	X														
Leukapheresis	X ^e				X ^{f,g}	X ^{f,g}			X ^f						

Evaluation	Study week (day window)														Early termination visit
	Screening ^a Week -6 to 0	Baseline Day 0	1 (± 4)	2 (± 4)	3 (± 4)	4 (± 4)	6 (± 4)	9 (± 7)	12 (± 7)	16 (± 7)	24 (± 7)	36 (± 7)	48 (± 7)	60, 72, 84, 96 (all ± 14)	

Administration of pembrolizumab ^h or placebo		X														
AE assessment			X	X	X	X	X	X	X	X	X	X	X	X	X ^c	X ^d
Blood draw for clinical/research labs, storage		X	X	X	X	X	X	X	X	X	X	X	X			X ^b

AE = adverse event; ECG = electrocardiogram; X = to be performed.

- a Screening can be scheduled over multiple visits per convenience of the participant and study team.
- b This assessment will only be conducted if the early termination visit is on or before week 48.
- c This assessment will be conducted over the phone.
- d This assessment will be conducted over the phone if the early termination visit is after week 48.
- e Will be performed after confirmation of eligibility. If the participant cannot do this procedure (eg, poor venous access), then an extra 80 mL of blood will be collected for storage and research.
- f This procedure is optional. If the participant declines to do it or cannot (eg, poor venous access), then an extra 80 mL of blood will be collected for storage and research.
- g Leukapheresis will be done at either week 3 or 4, not both. Scheduling will depend on the convenience of the participant and study team.
- h 200 mg via intravenous infusion for 30 minutes.

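### The fixed 12-week look-back at the week 60–96 calls is shorter than the longest interval the contact windows allow

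*Combined protocol and SAP*

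**What the plan says.** Section 6.3 schedules the late contacts and their window in one sentence: "Follow-up telephone calls at weeks 60, 72, 84, and 96 (± 2 weeks) will be conducted". The same sentence gives their purpose, "to see if any AEs potentially related to pembrolizumab occurred during the prior 12 weeks". Appendix B repeats the window as ±14 days for all four calls. The last clinic visit, at week 48, falls under the rule in Section 6.3 that "visits from week 9 onward will have a window of ± 7 days".

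Section 12.1 sets the reporting scope for this period: "Between weeks 48 and 96, reporting will be limited to only those SAEs and autoimmune events" that are at least possibly related to pembrolizumab. It also requires adverse events to be elicited at each contact, but gives no look-back length. Appendix B lists a medical history and medication review and an adverse event assessment by phone at the four calls, again with no look-back length. Section 6.4 provides for the telephone follow-up when a participant leaves between weeks 48 and 96, and gives it no recall period of its own.

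The Protocol Summary says participants will "be followed for safety for 96 weeks". Section 8.1 reports onset of immune-mediated complications "as late as 21 months after initiation of pembrolizumab".

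**The concern.** A 12-week look-back covers all the time since the previous contact only if contacts are never more than 12 weeks apart. The windows in the same section allow longer intervals. The reporting scope in Section 12.1 is continuous from week 48 to week 96, while the question specified for collecting those events may not be. No laboratory test or visit backs up the calls, so an event that goes unasked and unmentioned has no other scheduled route into the database.

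Safety is the primary objective, and the primary endpoint, which has no stated time limit, counts related Grade 2 or higher autoimmune events requiring corticosteroids. Such events also count towards a halting rule in Section 12.5. The pembrolizumab arm has 15 participants, so single events matter. The Clopper-Pearson upper 95% limit planned in Section 14 is 1 − 0.025^(1/15) = about 22% for 0 of 15. For 1 of 15 it solves (1−p)^15 + 15p(1−p)^14 = 0.025, giving about 32%.

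**Working it through.** **Inputs.**
- Nominal contacts at weeks 48, 60, 72, 84 and 96 (Section 6.3).
- Windows of ±1 week for the week 48 visit and ±2 weeks for each call (Section 6.3, Appendix B).
- Look-back of 12 weeks (Section 6.3).

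**The plan's own figure.** Each nominal interval is 12 weeks (60−48, 72−60, 84−72, 96−84). The 12-week look-back is therefore the nominal spacing, and coverage is complete when every contact is on its nominal date.

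**Longest interval within the windows.** Longest = nominal + early window of the earlier contact + late window of the later one. Uncovered = longest − 12.

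| Interval | Longest (weeks) | Uncovered (weeks) |
|---|---|---|
| Week 48 visit to week 60 call | 12 + 1 + 2 = 15 (e.g. weeks 47 and 62) | 3 |
| Any call to the next call | 12 + 2 + 2 = 16 (e.g. weeks 58 and 74) | 4 |

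The uncovered stretch lies just after the earlier contact. A later call cannot recover it, because its look-back starts later still.

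**Worst in-window total.** A late call cannot also be the early start of the next interval, so the maxima do not add across all four intervals. Enumerating in-window dates in one-week steps gives a maximum of 8 weeks, for example with contacts at weeks 47, 58, 74, 82 and 98. The look-backs are then 46–58, 62–74, 70–82 and 86–98. Weeks 58–62 and 82–86 are left out: 4 + 4 = 8, and 8/48 = 17%.

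**A typical value, under an assumption.** The documents do not say how contact dates fall within their windows. Suppose they are independent and uniform:
- Call to call, the mean uncovered time is 28/6 = 4.67 days, or 14.0 days over three intervals.
- For the first interval it is ½ × (14² + 7²/3)/28 = 3.79 days.
- The total is about 17.8 days per participant. Simulation gave the same figure.

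The possible range is 0 to 56 days.

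**Missed call.** On nominal dates, one missed call makes the interval 24 weeks and leaves 24 − 12 = 12 weeks uncovered. No section extends the next look-back.

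**Position of late onset.** 21 months × 365.25/12/7 = about 91 weeks, which is inside the telephone period.

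**The case against.** A reader might infer that there are periods nobody asks about. That goes too far, for three reasons.

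- Section 12.1 requires adverse events to be elicited at every contact, and Appendix B adds a history, medication and adverse event review at each call. Neither is capped at 12 weeks, and nothing tells staff to disregard an older event. An event in the gap remains reportable.
- Most events of interest would outlast the gap. For most of the immune-mediated events it covers with corticosteroids, Appendix A describes a taper over at least 4 weeks that starts only after improvement. An event that began after a week 58 call and was managed that way would still be under treatment after week 62, inside the look-back of a week 74 call. Thyroid deficiency and type 1 diabetes are described there with replacement treatment. The late hypophysitis case in Section 1.1 took 11 months to resolve.
- The sizes are upper bounds. The 8-week total needs calls alternating between opposite ends of their windows, and the 12-week figure needs a missed call, so it does not describe a participant with every contact in window.

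All of this stands, and it narrows the consequence. It does not remove the mismatch: the only look-back length in the protocol is the 12 weeks in Section 6.3, and no other provision overrides it. Appendix A is also guidance to be individualized, so event duration is no guarantee. What remains exposed is chiefly a related event that starts and resolves within the gap and goes unmentioned.

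**Conclusion.** The specified look-back does not match the contact windows or the continuous reporting scope for weeks 48–96. The shortfall is at most 4 weeks per interval (3 before the first call) and at most 8 weeks in total with all contacts in window. It disappears on nominal dates. The interval figures rest only on the stated dates and windows; the average of about 18 days rests on the assumed uniform timing. Severity is minor, and no sample-size, power or endpoint definition is affected.

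Two stronger conclusions might be inferred, and the documents do not support them. One is that late immune toxicity is the stated reason for following participants to week 96. Section 8.1 reports late onset but does not link it to the follow-up length, and no other section gives a reason. The other is that a 96-week safety claim in the analysis is overstated. Section 14 ties no analysis or claim to 96 weeks.

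**What to change.** In Section 6.3, replace the fixed 12-week look-back with *since the last completed study contact (visit or call)*, and record the date of that contact at each call. Uncovered time is then zero for any in-window dates. It is also zero after a missed call, provided a later call is completed. The same wording would serve the leaving call in Section 6.4. If a fixed period is preferred, it must be at least 16 weeks to cover in-window timing (15 is enough for the first call), but it would still fall short after a missed call.

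The cost is one sentence in the protocol, a matching edit to whatever call form is used, and one date field. No extra calls, visits or staff are needed, and the call windows, including that of the final call, can stay as they are.
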